3.1 TREATMENT FAILURE

Patients can discontinue the study treatment due to lack of efficacy and be declared a treatment failure if they have recurrence of ocular inflammation and/or recurrence of joint inflammation that is persistent and severe enough to necessitate unmasking to manage the arthritis recurrence.

Ocular inflammation is defined as ≥ 2 -step increase in AC cell from baseline, observed at 2 consecutive visits at least 7 days apart; $>0.5+$ AC cell for ≥ 28 days; $\geq 3+$ AC cell at a single visit; or $>0.5+$ vitreous haze, active retinal/choroidal lesions, or macular edema at a single visit.

Macular edema is defined as central subfield thickness on OCT > 2 standard deviations above normal thickness ($>320\mu\text{m}$ on Spectralis or $>300\mu\text{m}$ on Zeiss or Topcon) and having a greater than 20% increase from baseline *and/or* presence of intraretinal or subretinal fluid.

Patients with ocular inflammation that meets one of the treatment failure thresholds should return for an evaluation to evaluate whether the increased inflammation is sustained (called the Treatment Failure visit), as close to the 7- or 28-day period as possible, but no earlier.

Criteria for recurrence of ocular inflammation (at least one of the following in at least one eye)

Parameter	Definition
Anterior chamber cells*	≥ 2 -step increase** at two separate visits ≥ 7 days apart $>0.5+$ cell observed for ≥ 28 days $\geq 3+$ cell observed at a single visit
Vitreous haze***	$>0.5+$ haze at a single visit
Choroid & retina	Active retinal / choroidal inflammation and/or macular edema in either eye at a single visit. Macular edema is defined as central subfield thickness on OCT > 2 standard deviations above normal thickness ($>320\mu\text{m}$ on Spectralis or $>300\mu\text{m}$ on Zeiss or Topcon) and having a greater than 20% increase from baseline and/or presence of intraretinal or subretinal fluid

*SUN criteria; **increase is based on inflammation at baseline⁶⁰; ***NEI vitreous haze grading scale⁶¹

Patients who meet the treatment failure threshold of ocular inflammation at Month 12 will be re-evaluated after the Month 12 visit to assess for sustained inflammation which would result in treatment failure. If inflammation is sustained at the follow-up visit, then treatment failure is declared. At this point, patients and doctors will be unmasked, and doctors can treat per best medical judgement.

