6 STUDY INTERVENTION

6.1 STUDY INTERVENTION(S) ADMINISTRATION

6.1.1 STUDY INTERVENTION DESCRIPTION

Patients randomized to continue adalimumab will receive the standard clinical practice weight-based dose of adalimumab. The dosage and route of administration is self-administration of adalimumab subcutaneously at a dose of 40mg every other week for patients $\geq 30\text{kg}$ and 20mg every other week for patients $< 30\text{kg}$, which is in accordance with standard clinical practice and its FDA approved indication for treatment of JIA.¹⁷ Further detail on justification of dosing is provided in **Section 4.3**.

Patients randomized to stop adalimumab will receive placebo treatment. The volume-matched placebo will be administered subcutaneously for masking purposes every other week.

Adalimumab is commercially available in the U.S. for treatment of polyarticular JIA and non-infectious intermediate, posterior, and panuveitis in children 2 years of age and older at the aforementioned doses. Adalimumab is commercially available in the UK for treatment of both polyarticular and oligoarticular JIA in addition to chronic, pediatric anterior uveitis at the aforementioned doses. Adalimumab is commercially available in Australia for treatment of JIA and CAU at the aforementioned doses, with an exception of patients weighing less than 15kg receive 10mg every other week. Given that the use of adalimumab in patients with oligoarticular JIA and anterior uveitis is technically off-label, the Coordinating Center has obtained an Investigational New Drug Approval from the FDA.

The US formula of adalimumab has recently been changed to be citrate-free, which is the same formula that is in use in the UK. Following this announcement, AbbVie will be providing citrate-free adalimumab and placebo to all clinical study centers.⁶³⁻⁶⁵ To ensure the participants remain completely masked to treatment, the study will provide treatment kits to patients in both arms to standardize the appearance and labeling of adalimumab and the placebo.

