10.1.12.5 TRIAL SAFETY

A masked medical monitor at the CC has been appointed to evaluate the safety of the trial. All serious adverse events experienced by enrolled patients will be reported to the medical monitor in a timely manner, as defined in section 8.3.6. The medical monitor will determine expectedness of the patient's treatment and the reported event. The medical monitor will report his findings to the relevant entities defined in section 8.3.6.

The NEI's appointed DSMC will also review serious adverse events and general trial data on a 6-month basis, or as deemed necessary. Progress reports will be prepared for all scheduled DSMC meetings. An interim analysis will be performed and presented to the DSMC by the trial's unmasked biostatistician when approximately 40% of the trial's anticipated events have occurred. Whether or not to continue the trial will be based on this interim analysis. See **SAP section 3.7** for details on stopping.

On February 14th, 2024 the DSMC met, stopped enrollment and provided the following guidance for patients still completing follow-up in the trial:

- Patients should be told by the study investigator the results regarding efficacy of the continued administration of adalimumab for preventing recurrence of uveitis or arthritis.
- Patients are encouraged to remain in their assigned treatment group and complete follow-up, per protocol.
- Patients in active follow-up who have not yet been unmasked to their treatment assignment can be asked if they want to know their current treatment assignment.
- Patients receiving placebo may opt to discontinue their injections.

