Alternative models with interaction: tests of heterogeneity of effect. Consistency of effect between countries will be investigated. We propose to examine **homogeneity of treatment effect across countries** (by fitting survival models including country as a fixed effect along with treatment-country *interactions*). For the primary model and the aforementioned additional analyses of the primary

model, each will be repeated with an interaction term for country. All such analyses will be made available.

- As a sensitivity analysis, we will exclude treatment failures due to persistent and severe arthritis recurrence and assess the primary model with the recurrence of ocular inflammation only.
- We will examine treatment effect modification by disease type (JIA-associated uveitis vs. CAU) by fitting survival models including disease type as a fixed effect along with a treatment by disease type interaction. A further sensitivity analysis excluding individuals with CAU will be conducted. We acknowledge that these additional analyses may have low power since the trial is powered for main effects (not interaction) and excluding CAU patients will reduce the sample size. These analyses will also be made available.
- **Per-protocol.** We will conduct and report a per-protocol analysis excluding patients who missed 20% or more of their study medication.
- Our design yields failure times at discrete study visits. Statistically, we consider the failure time to occur at the first visit at which it is documented. A sensitivity analysis will be conducted in which we **impute the failure time** at the midpoint of the interval beginning with the last non-failure visit and the first failure visit.

Planned Secondary Analyses

Rationale. The proposed secondary analyses are intended to provide additional scientific information not present in the primary outcome and its analysis. These are of the following types: (1) use of the same outcome variable as the primary outcome, but at (a) different time points or (b) modeled by different covariates, and (2) use of different outcome variables.

- **The time to treatment failure, with censoring at 6 months**, a time to event outcome, will be analyzed using the template in the Primary Analysis above. This is the same outcome as for the primary outcome variable, except with observations restricted to 6 months.

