Futility. Early discontinuation due to the unlikeliness of significant findings conditional on interim results may be considered, based on the original sample size considerations. For evaluating futility, we propose discontinuation for futility if the conditional power to detect a hazard ratio of 2.0 for placebo/adalimumab (the original design effect) is below 20% at the interim analysis.³⁸ Conditional power will be derived by simulation of the unobserved future patients according to the original alternative hypothesis. Our proposed futility guidance is one-sided, and is subordinate to efficacy analyses.

Harm. Stopping for harm will be done at the judgment of the DSMC. Harm will be assessed using adverse events, and especially serious adverse events. Ethical considerations require careful consideration and judgment by the DSMC.

All subjects who provide informed consent will be accounted for in this study. We will present the number lost to follow-up and the number of protocol deviations by arm.

If the proposed stopping criteria are met from an efficacy standpoint and there are no safety concerns, enrollment will stop and patients who have already enrolled will be followed through their final visits following the current study protocol. Should they experience a treatment failure, they will be unmasked per protocol and can continue to receive study-provided medication through Month 12. Their outcomes are valuable to overall results (primary and secondary analyses). The trial's main result provides information which informs decision-making regarding the risks of stopping adalimumab. Patients who are enrolled have already made the decision that they are comfortable being randomized to stopping therapy, so they are already past the point of making that decision. Even if unmasked and on placebo, it would not be expected that such a patient would resume therapy if they did not experience a recurrence of inflammation.

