4.1 Summary

The following analysis populations are planned for this study:

- The **screening population**, which includes all patients who are screened for participation in the trial.
- The **safety population**, which includes all patients who received the intervention.
- The **intent-to-treat efficacy population**, which includes all patients who are randomized.
- The **per-protocol efficacy population**, which includes all patients in the intent-to-treat efficacy population, excluding patients with any of the following:
 1. Major protocol deviations, or 2. Noncompliance with study medications (more than 20% of the treatment missed).

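### The per-protocol rule has no exemption for placebo doses that patients could decline after 14 February 2024, so it can remove event-free stop-arm patients and raise the hazard ratio

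*SAP*

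**What the plan says.** The trial compares stopping adalimumab with continuing it. Placebo serves to hide the assignment: "The volume-matched placebo will be administered subcutaneously for masking purposes every other week" (Protocol 6.1.1).

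SAP 3.1.1 lists, among the subsidiary analyses of the primary model, a "per-protocol analysis excluding patients who missed 20% or more of their study medication". SAP 4.1 defines the per-protocol population by two exclusions: major protocol deviations, and "Noncompliance with study medications (more than 20% of the treatment missed". Both texts apply to both arms. Neither says over what period the 20% is counted.

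Protocol 10.1.12.5 records the guidance that the monitoring committee gave on 14 February 2024 for patients still in follow-up:

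- "Patients are encouraged to remain in their assigned treatment group and complete follow-up, per protocol".
- Patients "who have not yet been unmasked to their treatment assignment can be asked if they want to know" it.
- "Patients receiving placebo may opt to discontinue their injections".

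No matching option is given to the adalimumab arm. Patients who have failed have already left masked treatment: "At this point, patients and doctors will be unmasked, and doctors can treat per best medical judgement" (Protocol 3.1). SAP version 5 was written after the interim analysis and unmasking, and its revision history lists no change to the per-protocol rule.

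**The concern.** An adalimumab patient who misses doses moves away from the assigned strategy. A placebo patient who stops injecting does not, because that patient is still off adalimumab. The SAP makes the same assumption in section 3.7: "Even if unmasked and on placebo, it would not be expected that such a patient would resume therapy" without a recurrence.

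Only placebo patients who have not failed can use the option. If their declined doses count as missed, the rule removes event-free time from the stop arm and nothing comparable from the other arm. The per-protocol hazard ratio then rises for a reason unrelated to adherence to either strategy, and readers would take it as support for the intent-to-treat result. The comparison of missed doses between arms (SAP 2.3.3 and 3.1.3) would be distorted by the same doses.

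**Working it through.** **1. The plan's own figure.** The SAP 3.3.1 formula, with T = 48 weeks and medians of 20 and 10 weeks, has λ_C = ln 2/20 = 0.03466 and λ_I = ln 2/10 = 0.06931. Then φ(λ_C) = 0.001482 and φ(λ_I) = 0.004983. N per arm = (1.960 + 1.175)² × 0.006465 / 0.001201 = 52.9. Allowing for 10% loss, 2 × 52.9/0.9 = 117.6, or 118. Power with 59 × 0.9 per arm is 0.881. The planned 118 patients and 88% reproduce, so the same exponential model is used below.

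**2. When an opt-out becomes an exclusion.** Every-other-week dosing over 48 weeks is about 24 doses, and 20% of 24 is 4.8. With doses counted to failure or week 48, a patient who stops injecting at week u and is followed to week t has missed a share (t − u)/t. This reaches 20% when t ≥ 1.25u. A patient who stays event-free to week 48 is therefore removed if u ≤ 48/1.25 = 38.4. A patient who opts out at the same u but fails before 1.25u is kept. Exclusion depends on outcome even among those who opt out.

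The two thresholds can also give different answers. If 25 doses are scheduled (weeks 0 to 48 inclusive), 5 missed is exactly 20%, which SAP 3.1.1 excludes and SAP 4.1 keeps.

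**3. How many are removed.** Assumptions not in the documents:

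- 59 stop-arm patients, the planned number.
- Uniform accrual over the roughly 206 weeks from March 2020 to 14 February 2024.
- A share q of eligible patients opting out at that date.

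The expected number removed is q × (59/206) × (1 − e^(−48λ)) / (1.25λ), where λ is the stop-arm failure rate.

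- Median 10 weeks (λ = 0.06931): 0.2864 × 0.9641/0.08664 = 3.2 at q = 100%.
- 80% failing by 12 months, the SAP 3.3.2.1 expectation (λ = 0.03353): 0.2864 × 0.80/0.04191 = 5.5 at q = 100%.

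**4. Effect on the hazard ratio.** Simulation with 59 per arm, 3,000 runs per row, unadjusted Cox model, median hazard ratio (HR), and no other non-adherence:

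| Scenario | q | Removed | HR, all | HR, per-protocol |
|---|---|---|---|---|
| 10 vs 20 weeks | 25% | 0.8 | 2.00 | 2.02 |
| | 50% | 1.6 | 2.01 | 2.05 |
| | 100% | 3.2 | 2.01 | 2.12 |
| 80% stop-arm failure, HR 2 | 25% | 1.4 | 1.99 | 2.03 |
| | 50% | 2.7 | 2.00 | 2.06 |
| | 100% | 5.5 | 2.00 | 2.17 |
| No effect, 80% fail in each arm | 100% | 5.4 | 1.00 | 1.08 |
| No effect, 50% fail in each arm | 100% | 7.9 | 1.00 | 1.10 |
| No effect, 19% fail in each arm | 100% | 9.9 | 1.01 | 1.12 |

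The simulated counts at q = 100% agree with the formula in step 3. The rises in the HR 2 scenarios run from 2.02/2.00 (1%) to 2.17/2.00 (about 9%). Under no effect, the nominal 5% test rejects at most 6.5% of the time (4.7% before exclusion in that scenario). The 50% and 19% failure rates are assumed, to show a range.

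**5. With the exemption.** If declined placebo doses are not counted, or compliance is assessed only to 14 February 2024, this route removes nobody and the two hazard ratios coincide in the simulation.

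**The case against.** Several stronger readings are tempting, and the documents do not support them.

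- **That the per-protocol rule excludes only stop-arm patients.** It does not. Adalimumab patients who miss 20% are dropped too. Only the exclusions created by the guidance are one-sided.
- **That stop-arm patients who take adalimumab before failure stay in.** SAP 4.1 also excludes major protocol deviations, and the list in SAP 4.2 is open-ended, so these patients may be caught. Nothing commits to it, so it should be stated.
- **That the guidance urges placebo patients to stop.** It permits this, and the same list encourages patients to stay in their assigned group.
- **That removal is certain.** SAP 4.1 speaks of noncompliance, and stopping as the protocol allows can be read as compliant. That is fair, but SAP 3.1.1 speaks only of missed medication, and no text settles the matter.
- **That the bias must be upward.** The direction in the table depends on counting doses to failure or week 48. If all doses over 12 months were the denominator, early failures would themselves look non-adherent, and the bias could run the other way. Exclusion would still depend on outcome.

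The shift is also small. The largest change in the HR 2 scenarios is ln(2.17/2.00) = 0.08, against a standard error of about 2/√84 = 0.22. This stands, and it limits the importance of the point. Finally, SAP 3.7 says that after an early stop the final analysis uses the available data, while SAP 3.8 waits for all 12-month visits. Some doubt therefore remains about which data set the per-protocol analysis will use.

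**Conclusion.** The point holds within limits. Followed as written, with doses counted to failure or week 48, the rule removes stop-arm patients because they had not failed and raises the final per-protocol hazard ratio. Over opt-out shares of 25% to 100%, the rise is about 1% to 9% at the SAP's planning rates. A null ratio reaches about 1.1 if every eligible patient opts out.

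These sizes rest on 118 patients, uniform accrual and exponential failure times. The number of placebo patients still event-free on 14 February 2024 and the share who opted out are not in the documents. With fewer patients enrolled, the number removed falls in proportion.

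The intent-to-treat primary analysis is untouched. So is the interim result, because the guidance was issued at the meeting that reviewed it. The defect is confined to a subsidiary analysis and the missed-dose outcome, but it has a direction and is cheap to remove.

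**What to change.** In SAP 3.1.1 and 4.1:

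1. Count doses only up to treatment failure or week 48.
2. Do not count placebo doses declined under the 14 February 2024 guidance as missed. Alternatively, assess compliance only up to that date in both arms.
3. Use a single threshold in both sections.

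In SAP 4.2, state that adalimumab taken by a stop-arm patient before declared failure is a major protocol deviation. In SAP 3.1.3, apply the exemption in item 2 to the number of missed doses.

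A missed-dose rule for the continue arm alone is optional. It would compare adherent continuers with all stoppers, which could itself inflate the hazard ratio if adherence predicts outcome. If used, it should be labelled a sensitivity analysis.

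The cost is SAP wording and re-derivation of one population and one outcome. The Medication Adherence Log, the Interim Masking Decision Form and the Treatment Assessment Forms (Protocol 1.3) are already being collected. Because the change comes after unmasking, it should be dated and explained in the revision history.

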2.4 Randomization

2.4.1 Stratification

We propose stratification by country and use of antimetabolite medication. Within each stratum, assignments will be conducted using a randomly permuted block randomization scheme.

Patients will be enrolled in three countries: United States, United Kingdom and Australia. Patients will be recruited from fifteen to twenty study sites, with the possibility for sites to be added to meet the *fixed* sample size requirements. Patients will be randomized in a 1:1 ratio to two interventions: adalimumab or matched placebo. The treatment protocols are specified in the ADJUST Manual of Operations.

Stratification will be done by antimetabolite drug use based on a belief by the study team that concomitant antimetabolite drugs may have a differing impact on treatment outcomes of uveitis patients using TNF- α inhibitors.¹¹ Similarly, variations in the baseline demographics within each country may impact treatment outcomes with adalimumab.

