3.1 Analysis

3.1.1 Specific Aim 1

Primary Analysis

The prespecified primary analysis for Specific Aim 1 is Cox proportional hazards regression. The outcome variable is time to treatment failure, as defined in Section 2.3.1.

- The primary covariate of interest is the randomization group.
- Time to treatment failure is measured in the number of days since patient randomization.
- The parameter of interest is the hazard ratio of treatment failure comparing placebo (stopping) to adalimumab. We will estimate the hazard ratio and its 95% confidence interval using a fixed effect for treatment assignment in the Cox proportional hazards model.
- Hypothesis testing will be conducted by Monte Carlo permutation testing (see below for details).
- Tests will be two-sided, at prespecified type I error probability $\alpha=0.05$.
- Country and antimetabolite use will be included in the model as additional fixed effects, reflecting the stratified randomization.

Monte Carlo permutation testing. Hypothesis testing will be conducted using Monte Carlo permutation testing of the log hazard ratio coefficient estimated using the pre-specified primary analysis Cox proportional hazard model, based on 100000 replications (throughout this Statistical Analysis Plan). If the decision boundary lies within two standard deviations of the Monte Carlo estimate of the P-value, we will conduct one million replications and report the final value.¹⁴

Country. Any country with fewer than 5 enrollees will be aggregated with a similar country using a prespecified plan. Provided that we have fewer than 5 enrollees in Australia, we will aggregate them with the UK. Provided that we have fewer than 5 enrollees in the UK, we will aggregate them with Australia. If two countries experience fewer than 5 enrollees each, the US, the UK and Australia will be aggregated together.

Subsidiary Analyses of the Primary Model

Subsidiary analyses, or methodological sensitivity analyses, are conducted to assess the degree to which the choice of analytic method may have influenced the reporting of

the findings. Specifically, we mean: (a) choice of test statistic, (b) choice of estimation method, and (c) inclusion of covariates reflecting treatment site.

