- **The proportion of people with treatment failure over 6 months and 12 months**, a binary outcome, will be modeled using log binomial models to report relative risks. We will use the randomization group as a predictor. Clustered log-binomial regression will then be used to estimate the same regression model.
- **A decision tree model-based cost-effectiveness analysis will be conducted to assess adalimumab therapy.** The cost-effectiveness analysis will be conducted separately for the US, UK, and Australia. Healthcare costs will be gathered from appropriate US, UK, and Australia sources under the perspective of a third-party payer. In the US, costs will be estimated from the Medicare Physician Reimbursement Rates and the Red Book average wholesale prices. In the UK, costs will be estimated from the National Health System (NHS) reference costs published by the Department of Health. In Australia, costs will be estimated from the Medicare Benefits Scheme (MBS) reference costs. Each item will be multiplied by the unit cost associated with the item. We will consider the following

costs: (1) doctor visits, (2) procedural costs (e.g., OCT scans, laboratory tests, etc.), and (3) medications. Total costs per patients will be summarized in 2019 USD. Protocol-induced costs will not be included in the total patient costs as these are imposed by the trial protocol. We will use the following two measures of effectiveness: (1) time to inflammation recurrence during the 12-month study period and (2) gain in quality-adjusted life years (QALYs) over 12 months. Time to inflammation, or time to treatment failure, is defined in Section 2.3. The EQ-5D-Y from baseline, month 6, and month 12 will be used to calculate utility values ranging from 0 (equivalent to being dead) to 1 (perfect health). We will calculate the number of QALYs gained for each patient by estimating the area under the curve (AUC) using the three utility value estimates (e.g., baseline, month 6, and month 12).

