For continuous outcomes, plots of each measurement along with the outcome status will be prepared for each patient. Plots will include data for patients after any treatment failure, in a different color. We plan to separately examine patients using antimetabolites at baseline and those who were not. We will conduct linear mixed effects regression for these longitudinal outcomes, using time dependent covariates. The continuous variables of interest are:

- BCVA
- CHAQ score
- EYE-Q score
- JADAS-10 and JADAS-27 scores

Application of LASSO procedures to linear mixed models will be conducted with the R package `glmmlasso`.

Finally, a similar exploratory analysis will be used for the time to treatment failure (as defined earlier), again using LASSO regression with the same set of covariates. LASSO model selection will be implemented using the R package `coxnet`. We note that other model selection procedures (such as backwards stepwise regression) can be considered, provided uncorrected significance P-values are not reported after model selection.

3.1.3 Specific Aim 3

Primary analysis. The outcome variable is the proportion of people achieving corticosteroid-sparing controlled ocular inflammation at month 12 of the study. We propose log binomial regression, with randomization group as a covariate and fixed effects for baseline antimetabolite use and country. The analysis will follow the same template as in Specific Aim 1 for analysis of binary outcomes (including assessment of homogeneity by country). A linear binomial regression, with the identity link, will be used to calculate risk differences between groups. Significance will be assessed with a two-sided alpha of 0.05. The distinction between the analyses in Aims 1 and 3 are that in Aim 1, outcomes are reported at 6 and 12 months, censoring at treatment failure, while in Aim 3, outcomes are reported by intent-to-treat at 6 and 12 months, regardless of treatment changes in the event of treatment failure. We propose to use Firth bias correction in this log binomial regression, and additional information is provided below.

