Unmasking active patients at such an interim point compromises patient and personnel efforts already initiated towards the trial, as well as their study data. Enrolled patients will remain in the study. Enrollment, however, shall stop in an effort to disseminate study results sooner so that patients considering discontinuation of adalimumab can make better informed decisions about future treatment. The DSMC may reconsider the decision regarding the protocol for patients who have not completed their follow-up if/when stopping guideline criteria are met.

For the Statistical Analysis Plan, adverse event reporting will be descriptive in nature. Serious adverse events (SAEs) are reported directly to the medical monitor within 24 hours of the time the study site learns of them, and the medical monitor will subsequently pass this information on to the DSMC Chair. The medical monitor will receive notification of the event, the timing of the event, a medical narrative from the study site, the site location, and the patient identification number. The statistician will report the study treatment assignment to the DSMC Chair if deemed necessary by the DSMC. If use of either intervention clearly results in an unacceptable increase in the risk of treatment failures, then the study will be stopped.

In the event of that the DSMC stops the trial early, for any reason, the final analysis will be conducted on the available data.

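### The 6- and 12-month proportion failing has no single rule for patients censored before the time point and no Kaplan-Meier risk beside it; the bias is small unless follow-up is cut short

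*SAP*

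**What the plan says.** The first secondary objective of Aim 1 (SAP 2.3.1) compares the proportion failing over 6 and over 12 months. SAP 3.1.1, Planned Secondary Analyses, calls this a binary outcome that "will be modeled using log binomial models to report relative risks. We will use the randomization group as a predictor", and adds: "Clustered log-binomial regression will then be used to estimate the same regression model". It names no other covariate, no cluster unit, and no rule for a patient lost or censored before the time point.

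The general rules are in SAP 3.4:
- For time to failure, patients lost to follow-up are censored after their last visit.
- Secondary analyses use complete cases, assuming data are missing completely at random.
- Missing outcomes are handled by LOCF, with a sensitivity analysis of how extreme the missing values would have to be to change the conclusions.

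On the strata, SAP 2.4.1 says "We propose stratification by country and use of antimetabolite medication". The primary Cox model follows this: "Country and antimetabolite use will be included in the model as additional fixed effects, reflecting the stratified randomization". So does the Aim 3 binary model in SAP 3.1.3: "We propose log binomial regression, with randomization group as a covariate and fixed effects for baseline antimetabolite use and country". That section adds "The analysis will follow the same template as in Specific Aim 1 for analysis of binary outcomes", although the Aim 1 entry does not list those factors.

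On timing, SAP 3.7 says that after an early stop "the final analysis will be conducted on the available data". SAP 3.8 says all analyses are completed once every patient has had the 12-month visit.

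**The concern.** A patient censored at week 20 without failure is neither a failure nor a success at week 24 or 48. Complete case drops that patient but keeps those who failed early, so the risk is overstated. LOCF counts the patient as a non-failure, so the risk is understated. Neither uses the 20 weeks observed.

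The Cox analyses do use partial follow-up, but they give hazard ratios. I found no Kaplan-Meier or other censoring-adjusted absolute risk in the SAP, so the absolute risk of failure after stopping would come only from the binary model.

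Enrollment stopped on 14 February 2024 (Protocol 10.1.12.5) with patients still in follow-up. The SAP adapted other outcomes to this. SAP 3.1.1 added longitudinal models for visual acuity, JADAS, drug levels and antibody levels, and SAP 3.1.3 added a time-to-event analysis of regaining control because not all patients had reached month 12. The proportion failing received no such adaptation.

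**Working it through.** **1. The plan's own figure.** SAP 3.3.2.1 claims 80% power for a 28-point difference with 118 patients, taking 70% failing at 6 months and 80% at 12 months in the stopping arm. With 10% loss, 59 × 0.9 ≈ 53 per arm. A two-sided 5% test of proportions with continuity correction gives 78.2% power for 70% v 42% and 82.1% for 80% v 52%. The figure reproduces to within about 2 points, so sample size is not the issue.

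**2. Inputs for the bias.** Medians of 10 and 20 weeks (SAP 3.3.1) give λ = ln 2/10 = 0.0693 and ln 2/20 = 0.0347 per week. Dropout is η = 0.0022 per week (SAP 13.1). Time points are t = 24 and 48 weeks.

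**3. Formulas, exponential failure and dropout.**
- True risk: 1 − exp(−λt). Kaplan-Meier targets this.
- Observed failures: f = λ/(λ+η) × [1 − exp(−(λ+η)t)]. LOCF reports f.
- Failure-free completers: c = exp(−(λ+η)t). Complete case reports f/(f+c).

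Continuing arm at week 48: λ+η = 0.03686, so c = exp(−1.769) = 0.1705 and f = 0.9403 × 0.8295 = 0.780. Complete case is 0.780/(0.780+0.1705) = 0.821, against a true 0.811.

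| Week | Estimate | Stopping | Continuing | Relative risk |
|---|---|---|---|---|
| 24 | True | 81.1% | 56.5% | 1.435 |
| 24 | Complete case | 81.6% | 57.2% | 1.426 |
| 24 | LOCF | 79.5% | 55.2% | 1.440 |
| 48 | True | 96.4% | 81.1% | 1.189 |
| 48 | Complete case | 96.7% | 82.1% | 1.178 |
| 48 | LOCF | 93.8% | 78.0% | 1.202 |

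With follow-up completed, the arm-level bias is +0.3 to +1.0 points under complete case and −1.3 to −3.1 points under LOCF.

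**4. Analysis on data cut at the stop.** Assume uniform entry over the previous A weeks. The documents give no accrual pattern, so A runs from 100 to 204. The upper value is roughly the span from the planned March 2020 start to February 2024: 47 months × 4.35 ≈ 204 weeks. The integrand for f and the term c are then multiplied by (1 − s/A) and (1 − t/A). For A = 204, continuing arm, week 48: c = 0.1705 × (1 − 48/204) = 0.130 and f = 0.714, so complete case is 0.714/0.844 = 0.846.

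| A (weeks) | Estimate at week 48 | Stopping | Continuing | Relative risk |
|---|---|---|---|---|
| – | True | 96.4% | 81.1% | 1.189 |
| 204 | Complete case | 97.3% | 84.6% | 1.150 |
| 204 | LOCF | 88.1% | 71.4% | 1.234 |
| 100 | Complete case | 98.0% | 87.9% | 1.115 |
| 100 | LOCF | 82.2% | 64.5% | 1.273 |

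The two rules differ in the continuing arm by 84.6 − 71.4 = 13 points (A = 204) or 87.9 − 64.5 = 23 points (A = 100).

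**5. Low-failure continuing arm.** SAP 3.3.1 cites an adult open-label study with over 90% still inactive at week 54. Taking 10% failing by then, the true 48-week relative risk is 10.8. On cut data it would read 7.4–9.1 under complete case or 11.7–12.6 under LOCF.

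**6. Precision.** Over 4,000 simulated trials with planned dropout, the standard deviation of the stopping-arm risk (LOCF / complete case / Kaplan-Meier) was 0.052 / 0.052 / 0.052 at 6 months and 0.031 / 0.024 / 0.026 at 12 months.

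**7. Strata.** In 1,500 simulated stratified-block trials under each of two sets of assumed strong strata effects, the mean log relative risk was 0.375 adjusted and unadjusted in one setting, and 0.420 v 0.421 in the other. Empirical standard deviations differed by under 1%. The unadjusted model's standard error was about 3–5% too large.

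**The case against.** The case for leaving the plan alone has several parts.

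- **The SAP does handle censoring.** The primary Cox model censors and adjusts for the strata, and the 6-month time-to-failure analysis "will be analyzed using the template in the Primary Analysis above". This stands. A reader might infer that the SAP ignores censoring or that the main result is affected; it does not and is not. SAP 3.5 makes every analysis after each aim's primary descriptive.
- **The two missing-data rules may not conflict.** SAP 3.4 can be read as complete case for covariates and LOCF for outcomes, and SAP 3.2.3, which repeats complete case, is headed as being about covariates. That reading is possible but not stated. It would also select the rule with the larger bias here.
- **The planned scale is relative risk, which barely moves.** This stands for complete follow-up under the planned medians.
- **The large errors need an unplanned scenario.** SAP 3.7 also says enrolled patients are followed to their final visits, and the proportion failing is not among the outcomes adapted for the interim. The entry pattern is assumed and fits the planned accrual poorly. At A = 204, about (88.1 + 71.4)/2 = 80% have failed, so 34 events imply 34/0.80 ≈ 43 patients in 47 months, under one a month against the 3–4 anticipated in Protocol 5.5. The figures therefore illustrate sensitivity and do not forecast the result.
- **Kaplan-Meier is not assumption-free.** It needs non-informative censoring, which optional unmasking and stopping of placebo injections (Protocol 10.1.12.5) make less certain. This stands.

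Two further inferences are tempting and unsupported. One is that the planned model is generally less precise than Kaplan-Meier: step 6 shows equal precision at 6 months and a slightly smaller spread for complete case at 12 months. The other is that omitting the strata biases the relative risk: step 7 shows no such bias.

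**Conclusion.** The point holds in limited form. The secondary proportion failing is planned as if fully observed, the general rules give two answers for a patient censored failure-free, and no censoring-aware absolute risk is planned.

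If all patients complete 12 months and loss is the planned 10%, the harm is small: at most about 3 points in an arm's risk and about 1% in the 12-month relative risk. If the model is run on data cut at the early stop, the continuing-arm 48-week risk could read 85–88% or 65–71% against 81.1%, depending only on which rule is used. That range rests on exponential failure at the planned medians and on an assumed uniform entry over 100–204 weeks. SAP 3.7 and 3.8 do not settle which data set governs.

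The missing strata and the undefined cluster are matters of consistency and of being able to program the analysis. Adding the strata brings the model into line with the randomization and removes a slight conservatism in the standard errors. It does not remove bias.

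**What to change.** In SAP 3.1.1, Planned Secondary Analyses:

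1. Estimate the risk of failure at weeks 24 and 48 by Kaplan-Meier in each arm, censoring at the last visit as in the primary analysis. Report the risk difference and risk ratio with 95% confidence intervals.
2. If the log-binomial model is kept as support, state one rule for patients censored before the time point. Add country and antimetabolite use as fixed effects, to match the primary model and the Aim 3 binary model. With risks near 96% a log link may not converge, so point to the Poisson and logistic fallbacks already in SAP 3.2.2.
3. Name the cluster unit for the clustered version, or drop it. Each patient contributes one outcome per time point.
4. State whether SAP 3.7 or 3.8 governs the data set for this endpoint.

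The cost is SAP wording and a few lines of R, with no new data and no change to the primary analysis. Because enrollment has stopped and results are known, the change should be dated as made after the interim, as SAP version 5 does for its other additions. The remaining limitation is that Kaplan-Meier still assumes non-informative censoring, which the report should say.
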